**3.2 Registration – Exclusion Criteria**

3.21 Any of the following because this study involves an investigational agent whose genotoxic, mutagenic and teratogenic effects on the developing fetus and newborn are unknown:

- Pregnant women
- Nursing women
- Men or women of childbearing potential who are unwilling to employ adequate contraception as defined in [Section 9.0](#).

3.22 Receiving any other investigational agent which would be considered as a treatment for the primary neoplasm  
OR  
Participated in a study of an investigational agent, received study therapy or used an investigational device  $\leq 4$  weeks prior to registration

3.24 Immunocompromised patients and patients with known immunodeficiency; or receiving systemic steroid therapy or any other immunosuppressive therapy  $\leq 7$  days prior to registration.

NOTE: Inhaled steroids and low-dose corticosteroids are allowed (see [Section 9.0](#)).

3.25 History of active tuberculosis (TB), human immunodeficiency virus (HIV), active hepatitis B (e.g., HBsAg reactive) and/or active hepatitis C infection (e.g. HCV RNA qualitative is detected).

3.26 Received a live vaccine  $\leq$ 30 days prior to registration.  
NOTE: Seasonal influenza vaccines for injection are generally inactivated flu vaccines and are allowed; however intranasal influenza vaccines (e.g., Flu-Mist®) are live attenuated vaccines, and are not allowed.

3.27 Hypersensitivity to pembrolizumab, binimetinib, or any excipients of either drug.

3.28 Prior anti-cancer therapy with a monoclonal antibody (mAb)  $\leq$ 4 weeks prior to registration  
OR Failure to recover (to  $\leq$ Grade1) from adverse events (AE) attributable to agents received  $>$ 4 weeks prior to registration.

3.29a Prior therapy including chemotherapy, targeted small molecule therapy or radiation therapy  $\leq$ 2 weeks prior to registration  
OR Failure to recover (to  $\leq$ Grade1 or to baseline) from adverse events (AE) attributable to agents received  $>$ 4 weeks prior to registration.  
NOTE: Exception for neuropathy  $\leq$ Grade 2, which is allowed.

3.29b Any active central nervous system (CNS) lesion (i.e., those with radiographically unstable, symptomatic lesions) and/or leptomeningeal metastases.  
NOTE: Patients treated with stereotactic radiotherapy or surgery are eligible if no evidence of CNS disease progression  $\geq$ 4 weeks and patients must be off corticosteroid therapy for  $\geq$ 3 weeks.  
NOTE: Carcinomatous meningitis is excluded regardless of clinical stability.

3.29c Active autoimmune disease requiring systemic treatment in the past 2 years (i.e. use of disease modifying agents, corticosteroids or immunosuppressive drugs).  
NOTE: Replacement therapy (e.g., thyroxine, insulin, or physiologic corticosteroid replacement therapy for adrenal or pituitary insufficiency, etc.) is not considered a form of systemic treatment.

3.29d Known history of, or any evidence of active, non-infectious pneumonitis.

3.29e Active infection requiring systemic therapy.

3.29f Known history of acute or chronic pancreatitis.

3.29g History of or current evidence of retinal vein occlusion (RVO) or predisposing factors to RVO (e.g. uncontrolled glaucoma or ocular hypertension, history of hyperviscosity or hypercoagulability syndromes).

3.29h History of retinal degenerative disease.

3.29i History of Gilbert's syndrome.

3.29j Other active malignancy  $\leq$ 3 years prior to registration.  
EXCEPTIONS: Adequately treated non-melanotic skin cancer (adequate wound healing is required prior to study entry) or carcinoma-in-situ of the cervix.  
NOTE: If there is a history of prior solid tumor malignancy, it must have been treated curatively with no evidence of recurrence  $\leq$ 3 years prior to registration.

3.29k Impaired cardiovascular function or clinically specific cardiovascular disease including any of the following:

- History of acute coronary syndromes (including myocardial infarction unstable angina, coronary artery bypass grafting, coronary angioplasty, or stenting)  $\leq 6$  months; OR
- Symptomatic chronic heart failure history or current evidence of clinically significant cardiac arrhythmia and/or conduction abnormality  $< 6$  months prior to screening; except atrial fibrillation and paroxysmal supraventricular tachycardia.

3.29l Uncontrolled arterial hypertension defined as persistent elevation of systolic blood pressure  $\geq 150$  mmHg or diastolic blood pressure  $\geq 100$  mmHg despite medical treatment.

3.29m History of neuromuscular disorders that are associated with elevated CK (e.g., inflammatory myopathies, muscular dystrophy, amyotrophic lateral sclerosis, spinal muscular atrophy).

3.29n Planning to embark on a new strenuous exercise regimen after first dose of study treatment.  
Note: Muscular activities, such as strenuous exercise, that can result in significant increases in plasma CK levels should be avoided while on binimetinib treatment.

3.29o Impairment of gastrointestinal function or gastrointestinal disease (e.g., ulcerative disease, uncontrolled nausea, vomiting, diarrhea, malabsorption syndrome, small bowel resection).  
NOTE: Gastric bypass is allowed.

3.29p Any other condition that would, in the Investigator's judgment, contraindicate the patient's participation in the clinical study due to safety concerns or compliance with clinical study procedures, e.g., infection/inflammation, intestinal obstruction, unable to swallow medication, social/ psychological issues, etc.

3.29q Major surgery  $\leq 3$  weeks prior to registration or failure to adequately recover from surgery.

3.29r Medical, psychiatric, cognitive or other conditions that may compromise the patient's ability to understand the patient information, give informed consent, comply with the study protocol or complete the study

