#### 3.1 Registration – Inclusion Criteria

- 3.11 Age  $\geq$ 18 years.
- 3.12 Histological confirmation of adenocarcinoma of the breast.
- 3.13 Estrogen receptor (ER) and progesterone receptor (PR) negative; defined as ER $\leq$ 10% and PR $\leq$ 10% staining by immunohistochemistry (IHC).
- 3.14 HER2 negative in the primary or metastatic tumor tissue defined as:
  - Immunohistochemistry (IHC) Grade 0 as defined by no staining observed or membrane staining that is incomplete and is faint/barely perceptible and within  $\leq$ 10% of the invasive tumor cell; OR
  - IHC 1+ as defined by incomplete membrane staining that is faint/barely perceptible and within  $>$ 10% of the invasive tumor cell; OR
  - IHC Grade 2+ staining intensity by means of IHC analysis with no gene amplification below; OR
  - No gene amplification on ISH based on:
    - Single-probe average HER2 copy number  $<$ 4.0 signals/cell  
OR
    - Dual-probe HER2/CEP17 ratio  $<$ 2.0 with an average HER2 copy number  $<$ 4.0 signals/cell
- 3.15 For phase II part of the trial:  $\leq$ 3 prior lines of treatment in the metastatic setting for the current breast cancer. However, there is no limit on number of prior line of therapy in phase I part of the trial.
- 3.16 Measurable disease as defined in [Section 11.0](#).
- 3.17 ECOG Performance Status (PS) 0 or 1 ([Appendix I](#)).
- 3.18 The following laboratory values obtained  $\leq$ 14 days prior to registration.
  - Hemoglobin  $\geq$ 9.0 g/dL (Must be  $\geq$ 7 days after most recent transfusion)
  - Absolute neutrophil count (ANC)  $\geq$ 1500/mm^3 or  $\geq$ 1.5  $\times$  10^9/L
  - Platelet count  $\geq$ 100,000/mm^3 or  $\geq$ 100  $\times$  10^9/L (Must be  $\geq$ 7 days after most recent transfusion)
  - Total bilirubin  $\leq$ 1.5 x upper limit of normal (ULN)
  - Aspartate transaminase (AST) and alanine transaminase (ALT)  $\leq$ 2.5 x ULN or  $\leq$ 5 x ULN for patients with liver metastases
  - Creatinine  $\leq$ 1.5 x ULN  
OR
  - Calculated creatinine clearance must be  $\geq$ 50 ml/min using the Cockcroft-Gault formula below:

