General disorders and administration site conditions 
 
• Fatigue
 
	Grade 3 lasting $>$ 14 consecutive days
Skin and subcutaneous tissue disorders 
 
• Rash maculo-papular
 
• Palmar-plantar erythrodysesthesia syndrome
 
• Photosensitivity
 
	Grade 3 lasting $>$ 14 consecutive days despite maximal skin toxicity treatment per local practice Or Grade 4
Vascular disorders 
 
• Hypertension
 
	Grade 3 lasting $>$ 14 consecutive days Or Grade 4
Other events**	Any $\geq$ Grade 3

\*Adverse event at least possibly related to the study medication.

\*\* Lymphocyte count decreased  $\geq$ Grade 3 (unless clinically significant) and Grade 3 alopecia will not be considered a DLT

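### Exclusion 3.29a leaves therapy received only 15–28 days before registration outside both its washout limb and its toxicity-recovery limb

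*Combined protocol and SAP*

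**What the plan says.** Section 3.2, criterion 3.29a, joins two limbs by OR. The first excludes "Prior therapy including chemotherapy, targeted small molecule therapy or radiation therapy" received 2 weeks or less before registration. The second excludes failure to recover to Grade 1 or less "or to baseline) from adverse events (AE) attributable to agents received" more than 4 weeks before registration. One carve-out follows ("NOTE: Exception for neuropathy"), for Grade 2 or lower.

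Criterion 3.28, which begins "Prior anti-cancer therapy with a monoclonal antibody (mAb", has the same two-limb form, but both of its limits are 4 weeks.

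For phase I, 3.15 adds that "there is no limit on number of prior line of therapy in phase I part of the trial". Section 7.421 counts DLTs in Cycle 2 only. Its footnote sets the attribution threshold: "Adverse event at least possibly related to the study medication".

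**The concern.** A recovery rule should bind at least as tightly on recent therapy as on older therapy. As written, 3.29a asks for documented recovery from treatment that ended more than 4 weeks ago and is silent on treatment that ended 15–28 days ago, when residual toxicity is more likely. In 3.28 the same recovery limit sits next to a 4-week washout and leaves no hole. In 3.29a the washout is shorter and the recovery limit is unchanged.

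Two things are at stake. The first is entry safety: a patient could start binimetinib with unresolved non-laboratory toxicity that the criterion appears meant to screen. The second is attribution. Section 15.17 lists fatigue, rash, stomatitis and palmar-plantar syndrome among binimetinib's own toxicities, so an event carried in from prior therapy that then worsens is hard to call unrelated.

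**Working it through.** **The interval.** Let d be the days from receipt of prior therapy to registration, for therapy received only once or over a short course.

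| Criterion | Washout excludes | Recovery limb applies | Uncovered |
|---|---|---|---|
| 3.28 | d ≤ 28 | d > 28 | none |
| 3.29a | d ≤ 14 | d > 28 | d = 15 to 28, i.e. 28 − 14 = 14 days |

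Take two otherwise identical patients with ongoing Grade 2 hand-foot syndrome. At d = 30 the recovery limb excludes the patient. At d = 16 neither limb applies.

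**What other criteria cover.**
- 3.18: blood counts, liver, renal and coagulation values.
- 3.19a: LVEF and QTc.
- 3.17: ECOG 0 or 1.
- 3.22: a separate 4-week limit for investigational agents.
- 3.29o: gastrointestinal impairment, including uncontrolled nausea, vomiting and diarrhea.
- 3.29q: recovery from surgery.
- 3.29p: investigator judgment, with no grade threshold.

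None sets a general toxicity-recovery grade. What remains is mainly non-laboratory, non-cardiac, non-GI toxicity: fatigue, rash, hand-foot syndrome, mucositis.

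**Timing of the DLT window.** Treatment starts 0–14 days after registration (6.34), and Cycle 1 is 14 days of binimetinib alone (7.11). For a patient in the gap, Cycle 2 opens between 15 + 0 + 14 = 29 and 28 + 14 + 14 = 56 days after prior therapy, before visit windows or delays.

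**DLT thresholds (7.421).** Fatigue counts at Grade 3 lasting more than 14 consecutive days. Maculo-papular rash and hand-foot syndrome count at Grade 3 for more than 14 consecutive days despite maximal skin treatment, or at Grade 4. Mucositis falls under other events at Grade 3 or higher, with no duration rule. A stable Grade 2 residue is not a DLT under any of these.

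**Baseline grading.** 6.36 and 10.61 require baseline grading of listed symptoms. Fatigue and rash are on the list; hand-foot syndrome and mucositis are not, although the study calendar has a general adverse event assessment before registration. The DLT table refers to baseline only for CPK with creatinine and for LVEF, so no general rule says how a baseline grade enters DLT scoring.

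**Operating characteristics.** The 16.427 figures reproduce with P(pass) = (1 − p)³ + 3p(1 − p)² × (1 − p)³. At p = 0.10 this is 0.729 + 0.243 × 0.729 = 0.906 (stated 0.91). At 20, 30, 40 and 50% it gives 0.709, 0.494, 0.309 and 0.172 (stated 0.71, 0.49, 0.31, 0.17).

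**Sensitivity, by assumption only.** The documents give no carry-over rate. Suppose carried-over toxicity adds an independent DLT probability q per patient, so that the scored rate is 1 − (1 − p)(1 − q). The chance of passing a level is then:

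| | q = 0 | 5% | 10% | 15% |
|---|---|---|---|---|
| p = 10% | 0.906 | 0.824 | 0.730 | 0.632 |
| p = 20% | 0.709 | 0.622 | 0.536 | 0.454 |

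Here q averages over all enrolled patients, including those outside the gap. The table shows only the direction and steepness of the dependence. Level 0 is both the starting and the highest level (7.41), so a mis-scored DLT could only lower the selected dose.

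**The case against.** The best case for the plan has four parts.

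1. The recovery limb speaks of agents received more than 4 weeks before, not of the last dose. An agent given over several cycles and stopped 16 days ago was also received more than 4 weeks ago, so a site could reasonably require recovery. This stands as a narrowing of the gap. It leaves a short recent course, such as radiation or a newly started drug, uncovered. It also means that sites in a study that 16.1 calls multi-center could apply one criterion in two ways.

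2. A reader might infer that the gap distorts the MTD. The documents do not support that. To count, residual toxicity must persist or worsen to DLT grade about 29–56 days or more after prior therapy, mostly at Grade 3 or higher and sometimes for over 14 days, with at least possible attribution to study medication. Baseline grading helps attribution for the listed symptoms. Any stated fall in the chance of passing a level restates the assumed q.

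3. A reader might also infer that the gap feeds the phase II suspension rule in 16.52. That rule needs related events of Grade 4 or higher in 3 of the first 9 patients, or in 25% thereafter. Nothing in the documents links residual toxicity in an eligible ECOG 0–1 patient to that threshold.

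4. It is tempting to say that the 4-week figure is plainly the slip. The comparison with 3.28 shows that the limits do not fit together. It does not show which one was meant.

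**Conclusion.** The inconsistency is real and exact on a literal reading: a 14-day interval, days 15–28, in which 3.29a requires neither washout nor recovery. It matters mainly for entry safety and for attribution of non-laboratory, non-GI toxicity, where no other criterion sets a recovery grade.

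An effect on the Cycle 2 DLT count is possible but limited. Its size depends on how many patients enter in the window and how often their toxicity reaches DLT grade, and the documents give neither. The stated 3+3 probabilities are correct for the DLT rates they assume, and no alpha, power or sample size changes. The conclusion rests on reading the 4-week limit as applying to therapy received only within the window; for multi-cycle agents the text is ambiguous rather than silent.

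**What to change.** Reconcile the two time limits in 3.29a, and in the eligibility checklist, so that the washout and recovery limbs meet with no uncovered interval, as they do in 3.28. The sponsor should confirm which limit is intended; this review does not choose between them. Keep the baseline alternative in the recovery limb and the Grade 2 or lower neuropathy exception. Once the limbs meet, it no longer matters whether a site reads receipt as any dose or as the last dose.

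The cost is a short wording amendment and a checklist update. Some patients with unresolved toxicity would register later, once recovered, or not at all. That wait has no fixed upper limit. If the sponsor instead confirms the longer limit for the washout, patients last treated 15–28 days earlier would also wait, whether or not they have residual toxicity. No sample size or analysis changes.

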### 3.3 Retreatment Registration – Inclusion Criteria

3.31 Treatment cannot begin prior to registering to the retreatment phase and will ideally begin  $\leq 7$  days after registration for the retreatment phase.

3.32 Stopped initial treatment with pembrolizumab and binimatinib after attaining an investigator-determined confirmed CR according to RECIST 1.1, and:

- Was treated for at least 24 weeks with pembrolizumab and binimatinib before discontinuing therapy
- Received at least 2 cycles with pembrolizumab and binimatinib beyond the date when the initial CR was declared  
OR
- Had SD, PR, or CR and stopped pembrolizumab and binimatinib treatment after 24 months of study therapy for reasons other than disease progression or intolerance

3.33 ECOG Performance Status (PS) 0 or 1 ([Appendix I](#)).

3.34 Demonstrates adequate organ function. The following laboratory values obtained  $\leq 14$  days prior to re-registration:

- Hemoglobin  $\geq 9.0$  g/dL (Must be  $\geq 7$  days after most recent transfusion)
- Absolute neutrophil count (ANC)  $\geq 1500/\text{mm}^3$  or  $\geq 1.5 \times 10^9/\text{L}$
- Platelet count  $\geq 100,000/\text{mm}^3$  or  $\geq 100 \times 10^9/\text{L}$  (Must be  $\geq 7$  days after most recent transfusion)
- Total bilirubin  $\leq 1.5 \times$  upper limit of normal (ULN)
- Aspartate transaminase (AST) and alanine transaminase (ALT)  $\leq 2.5 \times$  ULN or  $\leq 5 \times$  ULN for patients with liver metastases
- Creatinine  $\leq 1.5 \times$  ULN  
OR
- Calculated creatinine clearance must be  $\geq 50$  ml/min using the Cockcroft-Gault formula below:

**Cockcroft-Gault Equation:**

$$\text{Creatinine clearance for males} = \frac{(140 - \text{age})(\text{weight in kg})}{(72)(\text{serum creatinine in mg/dL})}$$

$$\text{Creatinine clearance for females} = \frac{(140 - \text{age})(\text{weight in kg})(0.85)}{(72)(\text{serum creatinine in mg/dL})}$$

International Normalized Ratio (INR) or Prothrombin Time (PT) and activated Partial Thromboplastin Time (aPTT)  $\leq 1.5 \times$  ULN unless patient is receiving anticoagulant therapy as long as PT or PTT is within therapeutic range of intended use of anticoagulants

3.35 Females of childbearing potential should have a negative serum or urine pregnancy test  $\leq 72$  hours prior to re-registration.

3.36 Females or males of childbearing potential must be willing to use adequate methods of contraception as outlined in section 9.9b or abstain from heterosexual activity for the course of the study through 120 days after last dose of study medication.

3.37 Experienced an investigator-determined confirmed radiographic disease progression after stopping their initial treatment with pembrolizumab and binimatinib.

### 3.4 Retreatment Registration – Exclusion Criteria

- 3.41 Received any type anti-cancer treatment since the last dose of pembrolizumab
- 3.42 History or current evidence of any condition, therapy, or laboratory abnormality that might interfere with subject's participation for the full duration of the trial or is not in the best interest of the subject to participate, in the opinion of the treating investigator.

#### 4.0 Study Calendar

##### 4.1 Test Schedule for Breast Cancer

Tests and procedures			Active Treatment									End of Treatment	Post-Treatment
	$\leq 28$ days prior to registration	$\leq 14$ days prior to registration	Pre-Tx biopsy	Cycle 1 binimetinib alone	Cycles 2-3 with pembrolizumab		Cycles 4-8	Cycle 9	Cycle 10 and beyond	At time of disease progression	Safety follow up: 30 days post-discontinuation		
					Prior to C2 D1	Prior to C3 D1	Prior to Day 1	Prior to Day 1					
Window					$\pm 3$ days	$\pm 3$ days	$\pm 3$ days	$\pm 3$ days	$\pm 3$ days	$\pm 7$ days		$\pm 7$ days	
Clinical Procedures													
History and exam  , vital signs (temp, BP, heart rate), weight, ECOG PS	X				X	X	X	X	X	X		X	
Height	X												
Concomitant medications	X				X	X	X	X	X			X	
Pregnancy test 		X 											
Hematology: CBC/diff with PLT		X			X	X	X	X	X			X	
Chemistry Panel 		X			X	X	X	X	X			X	
CA15-3		X			X	X	X	X	X			X	
Creatine Kinase (CK/CPK), troponin T 4,R		X			X	X	X	X	X			X	
Urinalysis		X			X	X	X	X	X			X	
Coagulation INR (PT), PTT		X											
Total T3, Free T4, TSH R		X			X	X	X	X	X			X	
Tumor measurement by CT or MRI 	X						X						
Bone scan (only if clinically indicated)	X												

\*Retreatment Phase-Patients entering the study for retreatment will follow the test and procedures as indicated in the study calendar for Cycle 2 and beyond. Labs and blood forms are not required to be entered into RAVE during the Retreatment Phase.

 All tests and procedures are clinically indicated, unless noted with an R to indicate funding by research

 For women of childbearing potential only: Serum  $\beta$ HCG must be done  $\leq 7$  days prior to registration, and if necessary, again  $\leq 72$  hours prior to Cycle 1, Day 1

 AST (SGOT), ALT (SGPT), alkaline phosphatase, total bilirubin (direct if TBili is elevated), BUN, creatinine with calculated creatinine clearance, albumin, total protein, uric acid, bicarbonate, calcium, chloride, glucose, LDH, magnesium, phosphorus, potassium, sodium

 Follow up for total creatine kinase (CK/CPK)  $\geq 3$  X ULN will include weekly assessment of isoenzymes and myoglobin in blood/or urine, and troponin T as applicable

 Every 12-16 weeks after Cycle 4 during active treatment (per the treating physician's discretion). Same method should be used throughout the study. Note: PET/CT is not allowed as CT portion of PET/CT is not adequate for RECIST.

Tests and procedures			Active Treatment								End of Treatment	Post-Treatment
	$\leq 28$ days prior to registration	$\leq 14$ days prior to registration	Pre-Tx biopsy	Cycle 1 binimetinib alone	Cycles 2-3 with pembro		Cycles 4-8	Cycle 9	Cycle 10 and beyond	At time of disease progression	Safety follow up: 30 days post-discontinuation	
					Prior to C2 D1	Prior to C3 D1	Prior to Day 1	Prior to Day 1				
Window					$\pm 3$ days	$\pm 3$ days	$\pm 3$ days	$\pm 3$ days	$\pm 3$ days	$\pm 7$ days	$\pm 7$ days	
ECG, 12 lead, triplicate R	X					X						
Echocardiogram (ECHO)  – limited, LVEF only	X				X 		X 		X 		X	
Full ophthalmic evaluation 	X					X 	X 		X 		X	
Adverse event assessment	X			X	X	X	X	X	X	X	X	
Research Blood and Tissue- Analysis												
Blood for correlative research 8,R (See Section 14.0)			X		X	X		X			X	
Mandatory tissue sample (see Section 17.0) 9,10,R			X									
Optional follow up tissue sample(see Section 17.0) 11,R					X					X		

 Echocardiogram will be performed at baseline, on Cycle 2 Day 1, and Cycle 5 Day 1, then every 12 weeks to determine cardiac ejection fraction in patients who continue on binimetinib. Follow-up echocardiogram is not required in patients who discontinue binimetinib.

 Full ophthalmic examination will be performed at baseline, at Cycle 3 Day 1  $\pm 7$  days, and then every 12 weeks  $\pm 7$  days in patients who continue on binimetinib. Follow-up ophthalmic examination is not required in patients who discontinue binimetinib. Full ophthalmic examination includes best corrected visual acuity, slit lamp examination, intraocular pressure, dilated fundoscopy and Ocular Coherence Tomography (OCT). Examination of the retina is required, especially to identify findings associated with serous retinopathy and RVO. For patients with clinical suspicion of retinal abnormalities of any grade (e.g., serous retinopathy, RVO, photopsia, metamorphopsia, impairment of visual acuity), these additional assessments should be mandatory:

- For non-vascular abnormalities: spectral domain OCT recommended
- For Vascular abnormalities: fluorescein angiography of central 30 degrees.

 Whole blood samples for correlative research will be collected at the following timepoints: Baseline, 2nd week of binimetinib prior to starting pembrolizumab, After 1 cycle of bini and pembro at Cycle 3, Cycle 9, Day 1 (only if  $>6$  months of stable disease/CR/PR), and at the end of therapy (i.e.,  $\leq 4$  weeks after final administered dose of therapy), or at the time of tumor recurrence.

 Submission of tissue from the primary or metastatic tumor is mandatory

 Mandatory tumor biopsy except in patients who have adequate tumor tissue samples collected  $\leq 90$  days prior to registration. Adequate sample is defined as core needle, punch, or incisional biopsy samples that can provide  $\geq 10$  unstained sections of 5  $\mu$ M thickness. Fine needle aspiration (FNA) sample alone is not sufficient.

 An optional newly-obtained core or excisional biopsy (FNA not adequate) is requested after 10 days of binimetinib prior to starting pembrolizumab and at the end of treatment for any reason.

 Physical exam includes gross perimeter test. After baseline, patients receiving binimetinib should be assessed at every physical examination for decreased

Tests and procedures			Active Treatment								End of Treatment	Post-Treatment
	$\leq 28$ days prior to registration	$\leq 14$ days prior to registration	Pre-Tx biopsy	Cycle 1 binimeti nib alone	Cycles 2-3 with pembro		Cycles 4-8	Cycle 9	Cycle 10 and beyond	At time of disease progression	Safety follow up: 30 days post- discontinuation	
Window					$\pm 3$ days	$\pm 3$ days	$\pm 3$ days	$\pm 3$ days				
Patient Medication Diary (See Appendix II)				X		X	X	X	X	X		

---

visual acuity using a gross perimetry test (as opposed to automated visual field testing). Symptomatic patients should be referred for a full ophthalmic consultation.

